2.6.3. Accrual

Monitoring by the Protocol Team

The Protocol Team is responsible for continuous monitoring of study progress, including timely achievement of key milestones and quality of study conduct.

The team will closely monitor participant accrual based on reports that will be generated at least monthly. The team will monitor the timing of site-specific study activation, which will determine when each site will begin accruing participants and actual accrual following activation. For any site that is delayed in completing the study activation process or that falls short of its accrual projections, the team will work with the research assistant assigned to the site to identify the barriers the site has encountered and the operational strategies and action plans to address these.

The Protocol Team will similarly review key indicators of the quality of study conduct (e.g. data quality, and data and specimen completeness) based on reports and take action with study sites as needed to ensure high quality study conduct.

Monitoring

Operational futility may be considered if the observed accrual patterns are exceedingly different than planned, and the protocol team has had a chance to address the shortcomings of accrual.

3. AIM 2: PARTNER SELF-TESTING

3.1. OBJECTIVES

3.1.1. Primary Objectives:

- To determine whether providing index clients with HIV self-test kits for partners results in a greater number of partners tested as compared to optimized standard of care for partner notification and testing (referral slip)
- To determine whether providing index partners with HIV self-test kits is cost-effective compared to optimized standard of care using referral slips

3.1.2. Secondary Objectives:

- To assess the acceptability of giving self-test kits to index clients for partner testing
- To determine whether providing index partners with HIV self-test kits is superior to optimized standard of care in regard to identifying HIV+ partners (yield of testing)
- To determine whether providing index partners with HIV self-test kits is superior to optimized standard of care in regard to linkage rates among those who identify as HIV-positive
- To determine whether providing self-test kits to index clients and their partner is superior to optimized standard of care in regard to partner disclosure by the index client

3.2. STUDY POPULATION

This study will be conducted among approximately 1,800 individuals 15 years or older who have at least one sexual partner with unknown HIV status. The study population may include participants from Aim 1 who test HIV-positive under any of the three study arms.

The study will be conducted in the same 15 clusters used in Aim 1. The cluster randomization will be retained for Aim 2 such that sites identified as intervention sites for Aim 1 will remain intervention sites for Aim 2 (likewise for standard of care and optimized standard of care sites).

3.2.1. Inclusion Criteria

All of the criteria listed below must be met in order for an individual to be included in this study.

- At least 15 years of age or older
- Willing and able to provide informed consent for participation in this study
- HIV-positive
- Have at least one sex partner in the catchment area with an unknown HIV status at the time of study enrollment (defined as never testing for HIV or testing HIV negative more than 6 months ago)
- No history of intimate partner violence in the past 12 months
- No fear of intimate partner violence as a consequence of participating in the study
- Not enrolled in the INTERVAL study (no co-enrollment)

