3.2.2. Exclusion Criteria

Individuals will be excluded from the study if any of the following are identified during screening or any other time during the study:

[figure not shown]
- HIV-negative
- Younger than 15 years of age

- No sex partners with unknown HIV status in the catchment area at the time of study enrollment
- Experienced intimate partner violence during the past 12 months
- Fear of intimate partner violence as a consequence of participating in the study
- Enrolled in the INTERVAL study
- Unwilling or unable to provide informed consent

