3. **Partner self-testing arm:** Facilities randomized to partner self-testing will have study staff give self-test kits to index clients to distribute to every sexual partner with unknown status who lives in the facility catchment area within the prior 12 months (up to three sexual partners). They will also be given self-test kits for themselves so they can participate in couples testing if they choose. All index clients will be counseled on the importance of partner notification and testing and receive a demonstration on how to perform the self-test, so they can show partners. Self-test kits will contain information on how to use the test and a referral card. The referral card will contain information on where to present for confirmatory testing and where partners can receive ART, including a map to the facility. Index clients will be counseled to tell their partner to drop the completed test in a lockbox at the local health facility. A study phone number will also be provided in order to facilitate community-based collection of kits if participants are unwilling or unable to attend the facility. Written instructions, picture instructions, and maps will also be provided to the index client to give to the index partner. Index clients will also be counseled to encourage partners to present to the facility for routine HDA testing if they are unable or uncomfortable completing the self-test.

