3.3.2. Recruitment, Screening, and Enrollment Process

Standard of care arm

There will be no study “interventions” at the sites. A random subset of individuals will be recruited to complete a survey at the time they complete ART visits. Individuals will be screened to confirm they meet inclusion criteria, including having at least one partner of unknown status living within the facility catchment area at the time of their last clinical visit. After oral informed consent has been obtained, enrolled participants will complete a brief anonymous survey.

Optimized standard of care arm

Recruitment, screening, and enrollment will be the same as described above for standard of care sites.

Partner self-testing arm

Individuals will be recruited and initially screened by providers (HDAs and/or ART providers) who will identify HIV-positive clients 15 years of age and older with at least one partner who has unknown HIV status. Screening will be performed in a private space where no other clients or staff can hear the exchange of information. Eligible index clients will be referred to study staff for further screening (see 2.2.1 and 2.2.2 for inclusion/exclusion) and those who provide written informed consent will be enrolled.

1. Informed Consent

Written informed consent will be obtained before any study-specific procedures are performed. The informed consent process will include information exchange, detailed discussion, and assessment of understanding of all required elements of informed consent, including the potential risks, benefits, and alternatives to study participation. For standard of care and optimized standard of care arms (arms 1 and 2), informed consent will include a broad, general description of study objectives. Specific descriptions about the primary outcome of interest (index partner testing) will not be discussed in detail as the discussion may influence client behavior regarding partner testing, skewing findings. For the intervention arm (arm 3, self testing), the process will emphasize the randomized nature of the study and the differences that participants may experience as part of the study relative to current local standards of care.

2. Participant Withdrawal or Termination from the Study

Individuals may withdraw from the study at any time. Participants may also be terminated from the study by the site investigator or designee under the following circumstances:

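### The Aim 2 fear-of-violence criterion is tied to study participation, which means different things by arm, so it can select different clients for the self-testing and comparator arms

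*Combined protocol and SAP*

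**What the plan says.** Section 3.2.1 sets one list of Aim 2 criteria for all arms. It includes "No fear of intimate partner violence as a consequence of participating in the study", next to a separate criterion on violence in the past 12 months. Section 3.2.2 repeats both as exclusions and adds: "Individuals will be excluded from the study if any of the following are identified during screening or any other time during the study". Section 7.3 says more broadly that Aim 2 clients with any risk of partner violence are left out.

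What a participant does depends on the arm:

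- **Arm 3, self-testing (3.3.1, 3.4.4.1).** Facilities will "have study staff give self-test kits to index clients to distribute to every sexual partner with unknown status". The index client carries the kits to partners.
- **Arm 1, standard of care (3.3.2).** There is no study intervention; "enrolled participants will complete a brief anonymous survey".
- **Arm 2, optimized standard of care (3.3.2).** "Recruitment, screening, and enrollment will be the same as described above for standard of care sites". Providers give the referral slip at ART visits (4.2.1). Study staff approach clients as they leave and ask whether a slip was offered that day (3.4.2.2).

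Consent differs too. For arms 1 and 2, "Specific descriptions about the primary outcome of interest (index partner testing) will not be discussed in detail". For arm 3 it stresses how the study departs from usual care. Finally, the arm 3 recruitment text in 3.3.2 points staff to the wrong criteria: "see 2.2.1 and 2.2.2 for inclusion/exclusion".

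**The concern.** Aim 2's primary contrast is arm 3 against arm 2 (3.1.1). A client who is afraid to raise HIV testing with a partner has a clear reason to report fear when participating means handing that partner a kit. The same client in arm 2 is asked about the consequences of answering a survey. The slip is facility care that comes before enrolment and does not depend on it, and the consent talk says little about partner testing. That client has less reason to report fear, and so is more likely to be enrolled.

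This selection takes place after allocation in an unblinded trial, so randomizing facilities does not balance it. If fearful clients get fewer partners tested, removing them mainly from arm 3 raises its testing proportion relative to arm 2. The disclosure comparison is open to the same selection. Section 3.2.2 also lets the exclusion operate after enrolment, and the arm 3 follow-up survey asks about fear arising from the self-tests (3.4.4.4), so clients could be lost by that route as well.

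The plan has no fear question that is independent of arm, no comparison of exclusions by arm and no sensitivity analysis. The covariates named in the Aim 2 statistical section (5.1) do not include fear of violence.

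**Working it through.** **The plan's own figure.** Inputs from Aim 2, section 5.1: 20% in arm 2, 40% in arm 3, 600 clients per arm, 15 clusters (5 per arm, so 120 per cluster), ICC 0.004, type I error 0.05 (taken as two-sided).

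- Design effect = 1 + (120 − 1) × 0.004 = 1.476. Effective n = 600 / 1.476 = 406.5 per arm. Two-proportion power is above 99.9%, not the stated 89%.
- With ICC 0.04: design effect 5.76, effective n 104.2, power 88.9%.

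The printed ICC and the printed power do not agree. That is a separate matter, and the selection argument does not depend on it. Both ICC values are used below where they make a difference.

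**Size of the selection.** The documents give no input for this, so both quantities are assumptions:

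- f: the share of arm 2 clients who would be screened out under arm 3 conditions but are enrolled in arm 2
- q: the rate at which those clients' partners test

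If arm 2 were screened as arm 3 is, its rate would be (0.20 − f × q) / (1 − f). The bias is that rate minus 0.20. For example, f = 10% and q = 10% gives (0.20 − 0.01) / 0.90 = 21.1%, a bias of 1.1 points.

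| f | q | Comparable arm 2 rate | Contrast with 40% (points) | Bias toward self-testing (points) |
|---|---|---|---|---|
| 5% | 0% | 21.1% | 18.9 | 1.1 |
| 5% | 10% | 20.5% | 19.5 | 0.5 |
| 10% | 0% | 22.2% | 17.8 | 2.2 |
| 10% | 10% | 21.1% | 18.9 | 1.1 |
| 20% | 0% | 25.0% | 15.0 | 5.0 |
| 20% | 10% | 22.5% | 17.5 | 2.5 |
| any | 20% | 20.0% | 20.0 | 0 |
| 10% | 30% | 18.9% | 21.1 | −1.1 |

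The sign depends on q: positive below 20%, zero at 20%, negative above.

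**If self-testing had no effect.** Let 20% of partners test in both arms before screening, with q = 0. Arm 3 would then show 0.20 / (1 − f) = 21.1%, 22.2% or 25.0% for f = 5%, 10% or 20%. The chance of a significant result favouring self-testing is Φ[(d − 1.96 × SE₀) / SE₁], where SE₀ is the pooled and SE₁ the unpooled standard error at the effective n. For f = 20% and ICC 0.004: d = 0.05, SE₀ = √(2 × 0.225 × 0.775 / 406.5) = 0.0293, SE₁ = √((0.16 + 0.1875) / 406.5) = 0.0292, so (0.05 − 0.0574) / 0.0292 = −0.25, or 40.0%.

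| f | ICC 0.004 | ICC 0.04 |
|---|---|---|
| 5% | 5.6% | 3.8% |
| 10% | 11.8% | 5.9% |
| 20% | 40.0% | 13.6% |

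The nominal figure in that direction is 2.5%. These are large-sample figures that make no allowance for having only 5 clusters per arm, and q = 0 is the least favourable value.

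**The case against.** The best defence is that the protocol intends a common screen. The 12-month history criterion is the same in every arm and already removes many clients at risk. Section 7.3 excludes any risk without distinguishing arms. Comparator clients are not blind to the subject either: they are screened on having a partner of unknown status, asked how many partners qualify for slips, and later asked about disclosure and partner testing. In arm 3, kits are given only for partners to whom the client is willing to give one (3.4.4.1), so joining does not oblige anyone to approach a feared partner.

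All of this stands as reason to expect a modest f. None of it makes the fear item equal: 7.3 supplies no question, and the question that 3.2.1 does define still turns on participation.

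A reader might infer three stronger things that the documents do not support:

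- **That bias toward self-testing is established, or very large.** The documents say nothing about q, and the sign changes at 20%. A much larger bias needs a big fearful group left after the 12-month exclusion, no partner testing among them, and full exclusion in arm 3 with none in arm 2.
- **That arm 3's violence count will look falsely low against the comparators.** Section 5.1 plans no comparison of violence between arms. Follow-up in arms 1 and 2 asks only about violence arising from self-tests, which those arms do not hand out.
- **That the wrong cross-reference removes the violence screen in arm 3.** Sections 2.2.1 and 2.2.2 are the Aim 1 criteria, with no HIV-status, partner or violence item. But the sentence concerns HIV-positive clients with a partner of unknown status, section numbering is irregular throughout Aim 2, and 3.2.1, 3.2.2 and 7.3 all set the screen. It is a clerical error to correct, not evidence of bias.

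**Conclusion.** The point holds as a weakness in wording and screening. One criterion can select different clients by arm after unblinded allocation, and the plan has no means of detecting it or adjusting for it. The likely direction favours self-testing, on the reasonable but untested assumption that fearful clients' partners test at below 20%.

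The size is unknown. The illustrative range of 0.5 to 5.0 points rests on f of 5–20% and q of 0–10%. Under the printed ICC this would not threaten detection of a true 20-point effect: power is still 99.6% at the lowest contrast for q of 0–10%, 15.0 points. It would matter if the true effect were modest or nil.

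**What to change.** 1. Leave the existing safety exclusion as it is. Add one identically worded, arm-neutral item on fear of a partner's reaction to HIV testing. Study staff should ask it from one script at all 15 sites, beside the 12-month violence question, and record the answer before eligibility is decided.
2. Log exclusions by arm and reason, noting whether they occurred before or after enrolment, and report them.
3. Add a sensitivity analysis of arm 3 against arm 2 restricted, in every arm, to clients who report no fear on the common item. This reduces the imbalance but may not remove it, since the participation-specific exclusion still operates.
4. Reconcile 3.2.1 and 3.2.2 with 7.3, so that it is clear what counts as risk and whether that is the same in each arm. Which rule applies is for the sponsor and investigators to settle.
5. In 3.3.2, change the reference from 2.2.1/2.2.2 to 3.2.1/3.2.2.

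The cost is one question, one log field, one extra analysis and text corrections. The downside is slight possible priming of comparator clients, although they are already asked about partners of unknown status and slips. Imputing untested partners for clients excluded from arm 3 is not a good substitute: it would impose q = 0 on one arm only and needs partner data on people who never enrolled.

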3.2.2. Exclusion Criteria

Individuals will be excluded from the study if any of the following are identified during screening or any other time during the study:

[figure not shown]
- HIV-negative
- Younger than 15 years of age

- No sex partners with unknown HIV status in the catchment area at the time of study enrollment
- Experienced intimate partner violence during the past 12 months
- Fear of intimate partner violence as a consequence of participating in the study
- Enrolled in the INTERVAL study
- Unwilling or unable to provide informed consent

3.3. STUDY DESIGN

The study will utilize the cluster randomization of Aim 1 and compare use of HIV self-test kits for index clients to provide to partners compared with index partner testing using standard of care and optimized standard of care partner notification strategies (Fig. 3).

FIG 3: OVERVIEW OF STUDY DESIGN

3.3.1. Description of Randomization and Study Arms

Randomization from Aim 1 will be accomplished such that facilities randomized to the self-test intervention in Aim 1 will be self-test intervention sites for Aim 2 and sites randomized to standard of care and optimized standard of care for Aim 1 will continue as standard of care and optimized standard of care sites for Aim 2.

Description of Study Arms

1. **Standard of care arm:** Facilities randomized to the standard of care arm will use MOH approved referral mechanisms, without any intervention from the study team. Standard of care quality will vary by facility and may include some level of partner referral services for index partners such as referral slips. Referral slips may be given at HIV testing or ART clinics. Sites will be asked to counsel clients to have their partners bring referral slips back to the clinic to document the number of partners presenting for HIV testing. A random subset of HIV-positive clients in the standard of care arm will complete an anonymous survey to answer questions about whether they used referral slips and whether they know if partners came to a health facility for testing.

2. **Optimized standard of care arm:** Facilities randomized to optimized standard of care will be supported by the study team to systematically perform referral services following Ministry of Health Guidelines. Providers will receive an initial refresher training on partner testing followed by regular mentoring visits. Job aids will also be used to remind providers about the importance of partner testing. Standard of care procedures involve counseling HIV-positive individuals about the importance of partner testing and providing ‘referral slips’ to the index client to distribute to every sexual partner within the prior 12 months. Referral slips will be used to encourage partners to come to the facility for HIV testing. Sites will be asked to counsel clients to have their partners bring referral slips back to the clinic to document the number of partners presenting for HIV testing. A random subset of participants in the optimized standard of care arm will complete an anonymous survey to answer questions about whether they used referral slips and whether they know if partners came to a health facility for testing.
3. **Partner self-testing arm:** Facilities randomized to partner self-testing will have study staff give self-test kits to index clients to distribute to every sexual partner with unknown status who lives in the facility catchment area within the prior 12 months (up to three sexual partners). They will also be given self-test kits for themselves so they can participate in couples testing if they choose. All index clients will be counseled on the importance of partner notification and testing and receive a demonstration on how to perform the self-test, so they can show partners. Self-test kits will contain information on how to use the test and a referral card. The referral card will contain information on where to present for confirmatory testing and where partners can receive ART, including a map to the facility. Index clients will be counseled to tell their partner to drop the completed test in a lockbox at the local health facility. A study phone number will also be provided in order to facilitate community-based collection of kits if participants are unwilling or unable to attend the facility. Written instructions, picture instructions, and maps will also be provided to the index client to give to the index partner. Index clients will also be counseled to encourage partners to present to the facility for routine HDA testing if they are unable or uncomfortable completing the self-test.

3.3.2. Recruitment, Screening, and Enrollment Process

Standard of care arm

There will be no study “interventions” at the sites. A random subset of individuals will be recruited to complete a survey at the time they complete ART visits. Individuals will be screened to confirm they meet inclusion criteria, including having at least one partner of unknown status living within the facility catchment area at the time of their last clinical visit. After oral informed consent has been obtained, enrolled participants will complete a brief anonymous survey.

Optimized standard of care arm

Recruitment, screening, and enrollment will be the same as described above for standard of care sites.

Partner self-testing arm

Individuals will be recruited and initially screened by providers (HDAs and/or ART providers) who will identify HIV-positive clients 15 years of age and older with at least one partner who has unknown HIV status. Screening will be performed in a private space where no other clients or staff can hear the exchange of information. Eligible index clients will be referred to study staff for further screening (see 2.2.1 and 2.2.2 for inclusion/exclusion) and those who provide written informed consent will be enrolled.

1. Informed Consent

Written informed consent will be obtained before any study-specific procedures are performed. The informed consent process will include information exchange, detailed discussion, and assessment of understanding of all required elements of informed consent, including the potential risks, benefits, and alternatives to study participation. For standard of care and optimized standard of care arms (arms 1 and 2), informed consent will include a broad, general description of study objectives. Specific descriptions about the primary outcome of interest (index partner testing) will not be discussed in detail as the discussion may influence client behavior regarding partner testing, skewing findings. For the intervention arm (arm 3, self testing), the process will emphasize the randomized nature of the study and the differences that participants may experience as part of the study relative to current local standards of care.

2. Participant Withdrawal or Termination from the Study

Individuals may withdraw from the study at any time. Participants may also be terminated from the study by the site investigator or designee under the following circumstances:

- Site investigator or designee determines that continued participation in the study would be unsafe or otherwise not in the best interest of the participant
- The study is stopped or canceled by the sponsors, government or regulatory authorities, or site IRBs

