HIV Testing Services Program Officer
Ministry of Health, Dept of HIV/AIDS
Lilongwe, Malawi
Tele: [name]
Email: [contact]

[name]
Research Coordinator
Partners in Hope
[name], Lilongwe, Malawi

Use of HIV Self-Test Kits to Increase Identification of HIV-Infected Individuals and Their Partners

SCHEMA

Purpose: To evaluate the feasibility and cost-effectiveness of self-testing strategies within health facilities compared to standard of care in the following settings:
(1) group self-testing in outpatient departments (OPD) and sexually transmitted infection (STI) clinics compared to standard of care and optimized standard of care HIV testing and counseling; and
(2) self-testing for partners of HIV+ index clients compared to standard of care and optimized standard of care partner notification strategies.

Design: Unblinded cluster-randomized controlled trial

Study Population: Aim 1: Individuals 15 years of age and older not already known to be HIV-positive
Aim 2: HIV-positive individuals 15 years of age and older with at least one sexual partner with unknown HIV status

Sample Size: **Aim 1: 15 clusters with a total of 15,000 participants (5,000 per arm, 1,000 per site)**
Aim 2: 15 clusters with a total of 7,500 participants (2,500 per arm, 500 per site)

Intervention: Aim 1: To test the feasibility and cost-effectiveness of group HIV self-testing in outpatient department (OPD) and sexually transmitted infections (STI) clinics

- Arm 1: Standard of care for provider-initiated testing and counseling (PITC)
- Arm 2: Optimized standard of care for PITC
- Arm 3: Group HIV self-testing

Aim 2: To test the feasibility and cost-effectiveness of partner HIV self-testing

- Arm 1: Standard of care for partner testing
- Arm 2: Optimized standard of care for partner testing
- Arm 3: HIV self-testing

Study Duration: Approximately 18 months total

Aim 1: To test the feasibility and cost-effectiveness of group HIV self-testing for patients in waiting areas of outpatient department (OPD) and sexually transmitted infections (STI) clinics

Primary Objectives:

- To determine whether group self-testing in waiting areas of OPD and sexually transmitted STI clinics is superior in regard to number of individuals HIV tested compared to optimized standard of care (provider-initiated testing and counseling; PITC)
- To determine whether group self-testing in waiting areas of OPD and STI clinics is cost-effective compared to optimized standard of care using PITC

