4.3. Partner Self-Testing Arm

3.4.4.1 Baseline Visit for Index Client

A random sample of individuals will be screened and consented as they exit their ART visit. This will include ART clients who report having a sexual partner with an unknown HIV status. After written informed consent has been obtained, study staff will collect basic socio-demographics (including age, gender, marital status, and number of partners), HIV characteristics (date of HIV diagnosis, whether on ART and date started), and the number of eligible sexual partners they plan to give self-test kits.

The study staff will counsel the index client on how to administer an HIV self-test and will provide one self-test kit for each sexual partner within the last 12 months with unknown status (or HIV-negative more than 6 months ago) who lives within the catchment area of the facility and for whom the index client is willing to provide the test kit (up to three sexual partners). Index clients will also be given self-test kits for themselves if they wish to use them to complete couples counseling. All HIV self-test kits will be labeled with a unique ID linked to the index client participant. The ID will also be used to link index client survey responses with returned self-test kits.

The number of partners and the number of kits provided will be documented by study staff. Each self-test kit will be in a package that also contains a referral card. The referral card can be used for (1) those who test HIV-positive and need to present for confirmatory testing and link to care, (2) those who do not want to use the self-test kit and would rather test with an HDA, or (3) clients who experience difficulty or discomfort with the self-test kit and choose to test at a facility. The referral card will include information about the fa-

cility, including a map. The card will also contain a notation that if it is returned to another facility, the facility should contact the study team so that the card can be collected and recorded as “returned”. Study staff will periodically visit nearby testing sites to determine if any referral cards have been returned to those sites.

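### Aim 2 gives two incompatible entry routes for self-testing index clients; one would let unblinded providers filter entry in that arm only

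*Combined protocol and SAP*

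**What the plan says.** The Schema describes an "Unblinded cluster-randomized controlled trial". Sections 3.2 and 3.3.1 carry the Aim 1 facility allocation over to Aim 2, so each site's arm is known before any Aim 2 client is recruited.

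Section 3.3.2 sets out recruitment arm by arm:

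- Standard of care: "A random subset of individuals will be recruited to complete a survey at the time they complete ART visits".
- Optimized standard of care: "Recruitment, screening, and enrollment will be the same as described above for standard of care sites".
- Partner self-testing: "Individuals will be recruited and initially screened by providers (HDAs and/or ART providers) who will identify HIV-positive clients". It continues: "Eligible index clients will be referred to study staff for further screening". Those who give written consent are then enrolled.

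The sentence on further screening directs staff to the criteria with the words "see 2.2.1 and 2.2.2 for inclusion/exclusion".

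Section 3.4.4.1, the baseline visit for the self-testing arm, says: "A random sample of individuals will be screened and consented as they exit their ART visit". The baseline-visit sections for standard of care (3.4.1.2) and optimized standard of care (3.4.2.2) use the same sentence.

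On who may enter, section 3.2 adds: "The study population may include participants from Aim 1 who test HIV-positive under any of the three study arms".

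**The concern.** In a cluster trial, randomizing facilities does not protect the comparison if individuals are recruited differently once the arm is known. Section 3.3.2 describes such a difference: a provider-filtered group in the self-testing arm against a random ART-exit subset in the controls. Providers could, without intending to, refer clients they think more likely to approach a partner. HDAs work at the testing point, so their referrals could include more people at or near diagnosis, who may differ from established ART clients in disclosure and partner testing.

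At stake is the primary Aim 2 contrast, the proportion of partners tested under self-testing against optimized standard of care, and the cost-effectiveness results built on it. A larger sample does not remove a bias of this kind, and adjustment afterwards can only partly repair it.

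**Working it through.** **1. Entry route by arm, as written.**

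| Arm | Section 3.3.2 | Baseline-visit section |
|---|---|---|
| Standard of care | Random subset at ART visit | Random sample at ART exit (3.4.1.2) |
| Optimized standard of care | As standard of care | Random sample at ART exit (3.4.2.2) |
| Self-testing | Providers recruit and first-screen, then refer | Random sample at ART exit (3.4.4.1) |

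One cell differs. The self-testing arm matches the controls under 3.4.4.1 and does not under 3.3.2.

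**2. Can the two accounts be merged?** Only by adding something that the text lacks. Section 3.3.2 has no sampling step after referral. If staff sampled only from referred clients, the sampling frame would still be provider-filtered in one arm. No section requires providers to refer every eligible client or consecutive clients, and none asks for a log of those approached.

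**3. Bias under each reading.** Let w be the share of self-testing clients who enter through providers, and d the difference in partner-testing rate between such clients and a random ART-exit sample under the same arm conditions. Then bias = w × d.

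- Section 3.3.2 governs: w = 1, so bias = d.
- Section 3.4.4.1 governs: w = 0, so bias = 0.

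Neither section describes a mixture. The documents give no value or sign for d.

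**4. What a given d would do (illustration).** Inputs from section 3.5.1.1: 600 clients per arm, 15 facilities (5 per arm, so 600/5 = 120 each), type I error 0.05 (taken as two-sided), ICC 0.004, and 20% against 40% coverage.

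Design effect = 1 + (120 − 1) × ICC; n_eff = 600 / design effect. With p̄ the mean of p1 and p2, power = Φ{[|p2 − p1| − 1.96·√(2p̄(1 − p̄)/n_eff)] / √([p1(1 − p1) + p2(1 − p2)]/n_eff)}.

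The plan's own figure first. ICC 0.004 gives a design effect of 1.476, n_eff 406.5 and power above 99.9%, not the stated 89%. ICC 0.04 gives 5.76, 104.2 and 88.9%. That mismatch is a separate matter for the sponsor to check; here both ICCs are shown.

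The values of d below are assumptions. With no true effect (20% in both arms) and d positive, the chance of a significant result favouring self-testing, nominally 2.5%, is:

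| d (points) | Share of planned 20 points | ICC 0.004 | ICC 0.04 |
|---|---|---|---|
| +2 | 10% | 10% | 5% |
| +5 | 25% | 40% | 14% |
| +10 | 50% | 91% | 38% |

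With the planned 20% against 40% true and d negative, the power becomes:

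| d (points) | Apparent contrast | ICC 0.004 | ICC 0.04 |
|---|---|---|---|
| −2 | 20% v 38% | >99.9% | 82% |
| −5 | 20% v 35% | 99.8% | 68% |
| −10 | 20% v 30% | 91% | 38% |

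A t reference with 8 degrees of freedom lowers these somewhat: at ICC 0.004, the +5 and +10 entries become 33% and 83%.

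**5. Would the analysis correct it?** Section 3.5.1.1 evaluates arm differences with t-tests, rank tests, chi-square and Fisher's exact test, all unadjusted. It does plan hierarchical models with patient covariates, but to study factors associated with partner testing; they are not named as the arm comparison. Date of HIV diagnosis is collected at baseline in all three arms (3.4.1.2, 3.4.2.2, 3.4.4.1), so the covariate most relevant to the HDA route is available.

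**6. The cross-reference.** Sections 2.2.1 and 2.2.2 are the Aim 1 criteria: age and attendance at outpatient or STI services. They contain nothing on HIV status, partners or violence. The Aim 2 criteria are in 3.2.1 and 3.2.2.

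**The case against.** The strongest reply is that the operational section for the self-testing arm already prescribes the same random ART-exit sample as the controls, in the same words. A reader of 3.3.2 alone might infer that provider selection is the settled design. The documents do not support that: 3.4.4.1 says otherwise, and the bias arises only if 3.3.2 governs. This part of the reply stands.

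It is also fair that 3.3.2 has providers identify clients on stated criteria, with study staff screening again, so to say that providers hand-pick clients goes too far. Second-stage screening cannot, however, restore eligible clients who were never referred.

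The newly diagnosed route is an inference. HDA involvement is optional in the wording, section 3.2 admits Aim 1 positives from every arm, and newly diagnosed clients who start ART can also appear in an exit sample. It is a possibility, not a documented effect.

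Finally, a reader might take the wrong section pointer to mean that violence screening is omitted in Aim 2. It does not show that: 3.2.1 and 3.2.2 state the violence criteria, and section 7.3 repeats that those at risk are excluded. The pointer is an editorial error that should be corrected, and it is not evidence of selection bias.

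None of this settles which route sites should follow.

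**Conclusion.** The contradiction between 3.3.2 and 3.4.4.1 is certain from the text. The bias is conditional: zero if 3.4.4.1 governs, and equal to the unknown entry difference d if 3.3.2 governs. It would be tempting to attach a range in points, or to say that it favours self-testing, but the documents support neither. Provider-referred clients could test more partners or fewer. The figures above show only that an entry difference of 5 to 10 points, if it occurred, would matter for a planned 20-point contrast. They rest on assumed values of d, a normal approximation and equal cluster sizes. The point deserves correction before enrolment because differential entry cannot be fully repaired in analysis.

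**What to change.** - Reconcile the two sections: remove provider recruitment from 3.3.2 and use the random ART-exit sample of 3.4.4.1 in all three arms, run by study staff with one sampling and screening procedure.
- Log the numbers approached, eligible and consenting, by arm and site. This also matters because section 3.3.2 gives the arms different consent content, which identical sampling would not by itself even out.
- Prespecify an arm comparison that accounts for clustering and adjusts for time since HIV diagnosis, derived from the date already collected at baseline in every arm.
- Correct the eligibility cross-reference in 3.3.2 from 2.2.1 and 2.2.2 to 3.2.1 and 3.2.2.

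The cost is mainly protocol wording plus a recruitment log. Accrual in the self-testing arm may be slower. HIV-positive clients not yet attending ART would not be sampled, which narrows the population that section 3.2 allows but matches what already happens in the control arms.
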